#### Baseline data on previous MS DMD use and past treatment adherence

DMD treatments received in the 2 years prior to study enrolment (including medication doses and routes of administration, start dates, stop dates, and reasons for discontinuation) will be collected. A listing with the above characteristics and the date of diagnosis will be presented.

For each previous DMD received for MS during the last 2 years the corresponding number and percentage of patients that received it will be presented. The corresponding reasons (number and percentage) for discontinuation will also be reported.

The number of previous DMD received for MS (a) during the last 2 years and (b) in total will be summarized descriptively considering them as continuous variables.

For patients who were diagnosed with MS at least 12 months but less than 24 months prior to written informed consent, DMD treatments received since diagnosis will be summarized.

Past treatment adherence data will be collected before the first dose of cladribine tablets is taken. Data collected at Baseline through the modified Self-Injectables Version of the MS-TAQ to assess adherence during last previous injectable DMD treatment will be summarized descriptively to assess adherence during last previous injectable DMD treatment.

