| 2 | Version 3 | 06/19/2019 | Title page, Sections 4, 8.2, 9.1.1, 9.1.2.2, 9.3 and 9.7.4 | Clarified that retrospective data over the 24-month period prior to enrollment should be related to patients' MS diagnosis; thus, if a patient's diagnosis is <24 months, then data since diagnosis is collected | For added clarity |
| | | | Sections 4 and 9.2.1 | Changed inclusion criterion "Have time since diagnosis of RMS of at least 24 months" to "Have time since diagnosis of RMS of at least 12 months" | This inclusion criterion was updated based on site feedback and to expand the pool of eligible patients as a diagnosis of 1 year was deemed sufficient from a clinical perspective |
| | | | Sections 4 and 9.1.2.2 | Data on all previous DMDs since MS diagnosis (rather than only those received within 2 years prior to enrollment) will be collected | Data collection on previous DMDs has been expanded for a full picture on patients' treatment pathway since MS diagnosis |

| Amendment Number | Protocol Version | Date | Section of Study Protocol | Amendment or Update | Reason |
|---------------------|---------------------|------|--|--|---|
| | | | Title page, Sections 4, 7.4, 8, 8.1 and 9.2.1 | Clarified that indication for cladribine tablets is RMS, including RRMS and active SPMS | For added clarity |
| | | | Title page, Sections 4, 7.4, 8.2 and 9.7.3 | Re-phrased "physicians" treatment patterns" to "treatment patterns" | To clarify that MS treatment patterns are assessed, not comparisons of treatment patterns across physicians |
| | | | Section 11.1 | Added further definition for severe lymphopenia to include description of Grade 3 and Grade 4 lymphopenia | For added clarity |
| | | | Section 9.1.1 | Added additional recommendations from the USPI for when ALC drops to <200 cells per microliter | For added clarity |
| | | | Section 9.3 | Clarified that data on prior medication should be limited to MS symptomatic specific medications | For added clarity and to reduce site burden for data entry |
| | | | Section 9.1.2.2 | Added information that validated Spanish translations of PROs are available for this study; except for the PDDS for which a non-validated Spanish translation is used | For added clarity and transparency regarding the PDDS Spanish translation not being linguistically validated |

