8.2 Secondary Objectives

- To assess PROs, treatment adherence and treatment satisfaction during treatment with cladribine tablets
- To assess treatment patterns (MS treatment prior to transition to cladribine tablets, since MS diagnosis, concomitant treatment for MS during the last 2 years prior to initiation of cladribine tablets (or since MS diagnosis, if diagnosis <24 months), follow-up treatment in case of discontinuation of cladribine tablets)
- To estimate the ARR over the 24-month period prior to initiation of cladribine tablets (or since MS diagnosis, if diagnosis <24 months)

• To collect all serious adverse events (SAEs), adverse drug reactions (ADRs), adverse events of special interest (AESIs) and special situations during treatment with cladribine tablets over a 24-month period

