- Treatment adherence questions, based on modified versions of the Multiple Sclerosis Treatment Adherence Questionnaire (MS-TAQ); data to be collected via ePRO at baseline (modified for self-injectables to assess adherence during last previous injectable DMD treatment) and at the end of Months 1, 2, 13, and 14 (modified for cladribine tablets); a Spanish translation is available to patients.
- Proportion of patients experiencing a relapse. For this study, a relapse will be defined as determined and recorded by the investigator and information on the definition used by the investigator will be collected (see Section 9.1.2.1 for a guide on definition).
- Proportion of patients with relapse associated with hospitalization (relapse as primary diagnosis or reason for hospitalization). For this study, a relapse will be defined as determined by the investigator (see Section 9.1.2.1 for a guide on definition).
- Proportion of patients with relapse associated with glucocorticoid use. For this study, a relapse will be defined as determined by the investigator (see Section 9.1.2.1 for a guide on definition).
- Assessment of previous treatment for MS:
 - Previous DMD(s) received for MS prior to study enrollment, since MS diagnosis
 - Reasons for discontinuation of previous DMD(s)
- Proportion of patients who discontinue cladribine tablets
 - Reason for discontinuation of cladribine tablets
 - Elapsed time to discontinuation after first dose
 - Number of doses and % of planned doses (as per USPI) received
 - Subsequent treatment chosen following discontinuation of cladribine tablets
- Assessment of concomitant MS medications used during study period
- The ARR based on the last 24 months (or since MS diagnosis, if diagnosis <24 months) prior to the start of treatment with cladribine tablets (retrospective data). For this study, a relapse will be defined as determined by the investigator (see Section 9.1.2.1 for a guide on definition).

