9.3 Variables

The following variables will be collected:

Screening and/or Baseline Visit

- Patient demographics, including: age, sex, weight, self-reported race/ethnicity
- Date of diagnosis of MS, date of first symptoms of MS
- DMD treatments received prior to study enrollment, since MS diagnosis (including medication doses and routes of administration, start dates, stop dates, and reasons for discontinuation)
- Relapse of MS in the 2 years prior to the study period or since MS diagnosis, if diagnosis <24 months (including dates of onset and resolution of relapse)
- Most recent MRI results prior to starting cladribine tablets (baseline MRI), which is expected to have been taken within the prior 90 days (number of T1 Gd+ lesions; number of new T2 lesions compared to most recent prior MRI; number of newly enlarging T2 lesions compared to most recent prior MRI; number of CU lesions; presence of brain atrophy and segmental atrophy)
- Results of MRI in the 2 years prior to study enrollment or since MS diagnosis, if diagnosis <24 months (including prior documentation of number of T1 Gd+ lesions; new or newly enlarging T2 lesions; number of CU lesions; presence of brain atrophy and segmental atrophy)
- Results of neurological examination as per standard of care (e.g., Kurtzke Functional System Scores (FSS), ambulation up to 500 meters and Expanded Disability Status Score [EDSS])
- Results of physical examination as per standard of care
- Hematology assessment (white blood cell count, hemoglobin, hematocrit, platelet count, ALC). If the investigator assesses JCV status, these data should be recorded as well
- Pregnancy, human immunodeficiency virus (HIV), hepatitis B, hepatitis C and tuberculosis test results
- ePRO assessments (treatment adherence questions based on modified versions of the MS-TAQ, TSQM, SF-36, MFIS-5, BDI-FS, WPAI-MS, PDDS)
- Comorbid conditions
- List of all MS symptomatic specific medications taken in the 2 years prior to study enrollment (or since MS diagnosis, if diagnosis <24 months), including medication start and stop dates and reasons for discontinuation

Follow-Up Visits

The anticipated timing of assessments is presented in Table 1: Schedule of Assessments.

- Medication log of cladribine tablets treatment during the study period, including medication start dates, medication stop dates, medication dose (mg), number of dose and reasons for discontinuation

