Other relapse analyses	Proportion of patients experiencing a relapse (24-month and 12-month periods) and ARR over the 12-month period	24-month treatment period (or 30 months if Year 2 treatment is delayed) and 12-month	Section 14.2
	Proportion of patients with relapse associated with hospitalization and ARR associated with hospitalization		
	Proportion of patients with relapse associated with glucocorticoid use and ARR associated with glucocorticoid use	from first dose of cladribine tablets	
To assess treatment patterns (Multiple Sclerosis [MS] treatment prior to transition to cladribine tablets, since MS diagnosis, concomitant treatment for MS during the last 2 years prior to initiation of cladribine tablets (or since MS diagnosis if diagnosis <24 months), follow-up treatment in case of discontinuation of cladribine tablets)	
 
Assessment of previous treatment for MS:         
 
Previous DMD received for MS during the last 2 years
 
Number of previous DMD received for MS (a) during the last 2 years and (b) in total
 
Reasons for discontinuation of last previous DMD
 
 
 
Assessment of concomitant MS medications used during the study period
 
Proportion of patients who discontinue cladribine tablets         
 
Reason for discontinuation of cladribine tablets
 
Elapsed time to discontinuation after the first dose of cladribine tablets
 
Number of doses and % of planned doses of cladribine tablets aproduct Information [USPI]) received
 
 
 
Subsequent treatment chosen following discontinuation of cladribine tablets
 
	For previous treatment: 24- month period prior to initiation of cladribine tablets For concomitant medication, cladribine tablets discontinuation and subsequent treatment: 24- month period from first dose of cladribine tablets (or 30 months if Year 2 treatment is delayed)	Section 11.3 and section 12
To estimate the ARR over the 24-month period prior to initiation of cladribine tablets (or since MS diagnosis if diagnosis <24 months)	The ARR based on the last 24 months prior to the start of treatment with cladribine tablets (or since MS diagnosis if diagnosis <24 months) (retrospective data)	24-month period prior to initiation of cladribine tablets (or since MS diagnosis if diagnosis <24 months)	Section 11.3

Objectives	Endpoints (Outcome Measures)	Endpoints (Outcome Measures) Timeframe	IAP section

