## 7 Changes to the Planned Analyses in the Clinical Study Protocol

There are no changes to the planned analyses.

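### The SAP's visible by-drug table, listing and discontinuation reasons for prior DMDs stop at 2 years, while the protocol's secondary outcome runs from MS diagnosis

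*SAP*

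**What the plan says.** **Protocol.** The secondary objective in 8.2 covers "MS treatment prior to transition to cladribine tablets, since MS diagnosis". The 2-year window in that sentence belongs to concomitant MS treatment, not to prior treatment. The outcome list in 9.1.2.2 has "Previous DMD(s) received for MS prior to study enrollment, since MS diagnosis" and, beneath it, the reasons for stopping previous DMDs, in the plural and with no time limit. Section 9.3 collects "DMD treatments received prior to study enrollment, since MS diagnosis", including doses, routes, start and stop dates and reasons for discontinuation.

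**SAP.** Section 5 repeats the since-diagnosis objective. In the same row it defines the endpoint as DMDs received in the last 2 years, sets a 24-month timeframe for previous treatment, and limits the reasons to "Reasons for discontinuation of last previous DMD". The analysis-population table in Section 8.2 also describes treatment patterns over the last 2 years. Section 11.3 says that DMDs from the 2 years before enrolment will be collected and listed, then specifies the table: "For each previous DMD received for MS during the last 2 years the corresponding number and percentage of patients" who received it, with the corresponding reasons. It adds the number of previous DMDs in the last 2 years and in total. Section 7 states: "There are no changes to the planned analyses".

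**The concern.** The protocol names an outcome and has sites collect the data for it. The visible SAP analyses only a recent part of those data and does not say so. A programmer working from SAP 11.3 would leave out any drug that ended before the window, together with the reason it was stopped. The report would then describe recent DMD use under an objective worded as use since diagnosis. A reader could not tell which earlier drugs patients had tried or why they had left them.

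The SAP also gives two instructions on reasons for stopping: the last DMD only (Section 5), or each DMD in the 2-year window (Section 11.3). Neither is what the protocol specifies.

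**Working it through.** No sample-size, power or event figure is involved, and the plan states no figure to reproduce. The check compares the texts.

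| Item | Protocol 8.2, 9.1.2.2, 9.3 | SAP 5 | SAP 11.3 |
|---|---|---|---|
| Which DMDs, by name | Since diagnosis | Last 2 years | Last 2 years |
| Reasons for stopping | All previous DMDs | Last previous DMD | DMDs in the 2-year table |
| Listing | Not specified | Not specified | Last 2 years |
| Number of DMDs | Not specified | Last 2 years, and total | Last 2 years, and total |

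**Step 1: who can have a history longer than the window.** Protocol 9.2.1 requires at least 12 months since diagnosis and sets no maximum, so longer histories are admitted.

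**Step 2: how the SAP selects drugs.** The date-handling rules in SAP 9 ask whether a DMD was used within 24 months of study start. Selection is therefore by any use in the window; a long spell is not cut at 2 years.

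**Step 3: apply the rule to typical cases.**

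- Diagnosed 12 to under 24 months before consent: 11.3 summarizes DMDs since diagnosis, so nothing is lost.
- One DMD started 8 years ago and stopped last year: used in the window, so it is tabulated once with its reason. Nothing is lost.
- Two DMDs, the first stopped more than 2 years before enrolment: the first is in no by-drug table, no reasons table and no listing. It only adds 1 to the total count.
- Two DMDs, both used in the window: 11.3 reports two reasons, and Section 5 reports one.

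**Step 4: does the total count fill the gap?** No. It names no drug and gives no reason.

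**Step 5: does timing explain the mismatch?** The protocol's amendment log, used here only for the rationale, records under Version 3 (06/19/2019) that "Data on all previous DMDs since MS diagnosis (rather than only those received within 2 years prior to enrollment) will be collected". SAP version 1.0 is dated 11 July 2019, after that change, and the current SAP still has the 2-year window. The SAP's modification history mentions no decision to narrow it.

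**The case against.** Several points on the other side have force.

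- **Redaction.** SAP 5 assigns this objective to Section 11.3 and to Section 12, and Section 12 is blacked out. A since-diagnosis table there cannot be excluded. This stands, and it confines the point to the visible text. It does not remove the conflict, because the visible endpoint definition, timeframe, population table and Section 11.3 all depart from the protocol.
- **Partial reporting.** A reader might infer that the treatment-pattern outcome goes unreported. The documents do not support that. Drugs used in the last 2 years, their reasons and the total count are all planned, and SAP 13 covers stopping cladribine and the treatment that follows.
- **Size.** A reader might divide 2 years by the time since diagnosis and call the remainder lost history. That gives a share of calendar time, not of drugs or reasons lost: the 8-year spell above lies mostly outside the window, yet it is fully counted. Protocol 7.3 says most DMDs are continued unless ineffective or not tolerated, so spells that reach into the window are plausible. The documents give neither the distribution of time since diagnosis nor the number of DMDs stopped before the window.
- **Purpose.** A reader might infer that treatment sequence is the aim of this outcome. The protocol does not say so, and a by-drug frequency table would not show sequence.
- **SAP 7.** SAP 4 bases the plan on Protocol 9.7, and 9.7.3 mentions previous DMD treatment with no look-back period. The statement of no change can therefore be defended against that section alone. Even so, the SAP copies the since-diagnosis objective and then narrows it without comment.

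**Conclusion.** The point holds for the visible SAP. Its by-drug table, listing and reasons cover a shorter period than the protocol's secondary outcome, and Sections 5 and 11.3 disagree on reasons. The consequence is partial reporting: DMDs stopped more than 2 years before enrolment are reduced to a contribution to a count.

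The loss is zero for patients diagnosed less than 24 months before consent and for those whose DMDs all reach into the window. For the remaining patients it cannot be sized from the documents. The conclusion assumes that redacted SAP section 12 does not already supply the missing table.

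The item is descriptive and secondary, carries no test, and leaves the primary annualized relapse rate untouched. It should be corrected before the final tables are produced, but it does not threaten the trial's main result.

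**What to change.** In SAP 5, 8.2 and 11.3, list and tabulate each previous DMD and its reasons for discontinuation since MS diagnosis, and change the Section 5 timeframe for previous treatment to match. Keep the 2-year table as a labelled subset. Reword the reasons endpoint in Section 5 so that it covers the same drugs as 11.3. If the 2-year restriction is intended, state and justify it in SAP 7 instead; the Section 5 and 11.3 wording on reasons would still need to agree. If Section 12 already holds a since-diagnosis table, refer to it from Sections 5 and 11.3.

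The cost is one extra table, a wider listing and SAP wording. Protocol 9.3 already collects the data, so sites have nothing new to do.

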#### Pregnancy and comorbid conditions

The number and percentages of patients with positive result will be reported for the following tests, if performed at baseline: Pregnancy, HIV, hepatitis B, hepatitis C, tuberculosis and JCV tests.

CCI			
	-		
	_		
	=		
			
CCI			
001			

## **13** Study Dose Compliance and Exposure

All dosing calculations and summaries will be based on the "Exposure" eCRFs pages.

The FAS (i.e., Safety) population will be used for the related summaries.

The number of planned 10 mg tablets will be determined as follows (where weight is in kg and refers to the baseline weight).

For patients in the initial treatment course in Year 1, for each treatment week:

- 1. If weight <110 then 'Number of planned tablets' = nearest integer to (weight -5)/10
- 2. If weight  $\geq = 110$  then 'Number of planned tablets' = 10

For patients in the second treatment course in Year 2, for each treatment week:

- 1. If weight < 80 then 'Number of planned tablets' = nearest integer to (weight -5)/10
- 2. If weight  $\geq 80$  and weight <110 then 'Number of planned tablets' = nearest integer to (weight 15)/10
- 3. If weight  $\geq = 110$  then 'Number of planned tablets' = 10

The planned dose (mg) is given by 'Number of planned tablets '\*10.

The planned dose (mg/kg) is given by 'planned dose (mg)'/weight.

For each treatment week the actual number of tablets received is given by the 'Number of tablets' as recorded through the eCRF forms.

The actual dose (mg) is given by 'actual number of tablets '\*10.

The actual dose (mg/kg) is given by 'actual dose (mg)' /weight.

Treatment adherence is one of the secondary endpoints and will be assessed through a questionnaire. It will be described in section 16.4.

Data on cladribine tablets treatment during the study period will be collected, including medication start dates, medication stop dates, medication dose (mg), number of doses and reasons for discontinuation, if applicable. A listing with at least the following characteristics will be presented:

- Patient ID
- Cladribine tablets Start Date
- Cladribine tablets Stop Date
- Visit
- Planned number of tablets
- Actual number of tablets
- Planned dose (mg/kg)
- Actual dose (mg/kg)
- Treatment compliance (%)
- Reason for dose adjustment
- Reason for no dose

The number of planned tablets, the planned dose (mg/kg) and the actual dose (mg/kg) will be provided. Treatment Compliance (%) is defined as Total actual number of Cladribine tablets / Total planned number of Cladribine tablets.

The number and percentage of patients who discontinue cladribine tablets will be reported.

The number and percentage of patients who started another MS treatment after discontinuation of cladribine tablets will be reported (using the number of patients who discontinue cladribine tablets as denominator).

Reasons for discontinuation of cladribine tablets will be collected and for each reason, the corresponding number and percentage of patients will be reported (using the number of patients who discontinue cladribine tablets as denominator).

A listing of concomitant MS medications started after discontinuation of cladribine tablets will be provided. The following variables will be reported:

- Patient ID
- Medication name
- Visit
- Dose
- Unit
- Frequency
- Route of administration
- Start Date / Ongoing (Yes/No) / Stop Date
- Last study treatment administration date

The elapsed time to discontinuation of cladribine tablets will be calculated as:

*elapsed time to discontinuation of cladribine tablets = Date of discontinuation of cladribine tablets – Date of first study dose* 

It will be summarized as a continuous variable and also reported through a KM analysis. The 'Last study treatment administration date' according to the Treatment Termination form will be used as date of discontinuation of cladribine tablets (both for patients early discontinuing the treatment and for patients completing the treatment; for patients completing the treatment this will be a censoring date).

Number of doses and % of planned doses (as per USPI) received will be summarized descriptively.

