9.2.2 Definition of Study Cohorts and Description of Treatments

The study will have a single cohort that consists of all patients enrolled in the study who received at least 1 dose of cladribine tablets. All treatment and other medical decisions will be made by the investigator.

All study patients are anticipated to receive marketed cladribine tablets as per investigator discretion and as per US approved label: 3.5 mg/kg body weight over 2 years, administered as 1 treatment course of 1.75 mg/kg per year. Each treatment course consists of 2 treatment weeks, 1 at the beginning of the first month and 1 at the beginning of the second month of the respective year. Each treatment week consists of 4 or 5 days on which a patient receives 10 mg or 20 mg (1 or 2 tablets) as a single daily dose, depending on body weight. Since prescribing is determined by the investigator as per standard of care and according to the USPI, the benefits and risks to patients in being in the study are not different than the benefits and risks to patients taking cladribine tablets as per standard of care and according to the USPI in the general population.

Following completion of the 2 treatment courses, do not administer treatment during the next 2 years as stated in the USPI.

As per USPI, ALC values need to be normal at the initiation of cladribine tablets in Year 1, and ALC results need to indicate \geq 800 cells per microliter at the start of the Year 2 treatment course. If necessary, the Year 2 treatment course should be delayed for up to 6 months to allow for recovery of lymphocytes to \geq 800 cells per microliter. If this recovery takes more than 6 months, the patient should not receive further treatment with cladribine tablets.

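### For baseline weight 80 to <110 kg, SAP 13 plans one more tablet per treatment week in Year 1 than in Year 2, although the protocol sets the same 1.75 mg/kg course each year

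*SAP*

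**What the plan says.** Protocol 9.2.2 gives the regimen as "3.5 mg/kg body weight over 2 years, administered as 1 treatment course of 1.75 mg/kg per year". On the structure of a course it says "Each treatment course consists of 2 treatment weeks, 1 at the beginning of the first month", with the second week at the start of the second month. It also says "Each treatment week consists of 4 or 5 days on which a patient receives 10 mg or 20 mg (1 or 2 tablets", according to body weight. It describes no lower dose in Year 2.

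SAP 13 turns this into planned 10 mg tablets by formula, "where weight is in kg and refers to the baseline weight". For Year 1 the rule for each treatment week is "If weight <110 then 'Number of planned tablets' = nearest integer to (weight -5)/10", and 10 tablets from 110 kg. A separate block begins "For patients in the second treatment course in Year 2, for each treatment week". It keeps the Year 1 rule below 80 kg and the 10 tablets from 110 kg, but for 80 to <110 kg it replaces the 5 by 15.

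On outputs, the SAP says "The number of planned tablets, the planned dose (mg/kg) and the actual dose (mg/kg) will be provided". It also says "Treatment Compliance (%) is defined as Total actual number of Cladribine tablets / Total planned number of Cladribine tablets". SAP 7 declares no change from the analyses planned in the protocol.

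**The concern.** A patient of a given baseline weight has the same mg/kg target in both years, yet in one weight band the SAP plans fewer tablets for the second course. Neither document gives a reason. A change in weight cannot be the reason, because baseline weight is used throughout.

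Planned tablets and planned mg/kg are promised in a listing and a summary. For this band they would show a planned Year 2 dose reduction that the protocol does not describe. The same counts are the denominator of compliance, and the natural basis for the secondary outcome on the percentage of label-planned doses received. A fully dosed patient could look under-dosed in Year 1 and over-dosed in Year 2 if either figure is produced by course.

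**Working it through.** **Inputs.** Year 1 and Year 2 rules, baseline weight and 10 mg tablets: SAP 13. Two treatment weeks per course, 1.75 mg/kg per year, and at most 5 days of 2 tablets per week: Protocol 9.2.2. Halves are rounded up; rounding halves to even would change only weights of exactly 80, 90 or 100 kg.

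**Sign in the Year 2 rule.** The sign before 15 is missing from the text as extracted, which is not an error in the plan. At 85, 95 and 105 kg, (weight + 15)/10 gives 10, 11 and 12 tablets per week; (weight − 15)/10 gives 7, 8 and 9. The protocol's ceiling is 5 × 2 = 10 per week, so only minus fits.

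**Plan by weight band.** Tablets per course = 2 × weekly count. Planned mg/kg = 10 × tablets / weight, shown at 85, 95 and 105 kg.

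| Weight (kg) | Weekly, Y1 / Y2 | Course, Y1 / Y2 | mg/kg, Y1 / Y2 | Two-year tablets | Two-year mg/kg |
|---|---|---|---|---|---|
| 80–<90 | 8 / 7 | 16 / 14 | 160/85 = 1.88 / 140/85 = 1.65 | 30 | 300/85 = 3.53 |
| 90–<100 | 9 / 8 | 18 / 16 | 180/95 = 1.89 / 160/95 = 1.68 | 34 | 340/95 = 3.58 |
| 100–<110 | 10 / 9 | 20 / 18 | 200/105 = 1.90 / 180/105 = 1.71 | 38 | 380/105 = 3.62 |

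In 0.1 kg steps from 40 to 139.9 kg, the years differ at all 300 steps from 80.0 to 109.9 kg, always by 1 tablet per week, and nowhere else.

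**Size if the SAP totals are split equally (assumption).** The yearly counts become 15, 17 and 19.
- Year 1: 16/15 = +6.7%, 18/17 = +5.9%, 20/19 = +5.3%.
- Year 2: 14/15 = −6.7%, 16/17 = −5.9%, 18/19 = −5.3%.
- Planned dose per year is off by 10 mg: 10/85 = 0.118, 10/95 = 0.105 and 10/105 = 0.095 mg/kg.
- Odd yearly counts need unequal weeks (8+7, 9+8, 10+9). One week of each year is then right and the other is off by 1 tablet.

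**Compliance of a fully dosed patient on that split.**
- By course, Year 1: 15/16 = 93.8%, 17/18 = 94.4%, 19/20 = 95.0%.
- By course, Year 2: 15/14 = 107.1%, 17/16 = 106.3%, 19/18 = 105.6%.
- In the affected week only, Year 1: 7/8 = 87.5%, 8/9 = 88.9%, 9/10 = 90.0%.
- In the affected week only, Year 2: 8/7 = 114.3%, 9/8 = 112.5%, 10/9 = 111.1%.
- Both years: 30/30, 34/34, 38/38 = 100%.

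**Range if one year's rule is right for both years instead.**
- Year 1 rule in both years: totals 32, 36, 40 (320/85 = 3.76, 360/95 = 3.79, 400/105 = 3.81 mg/kg). The Year 2 plan is 2 tablets low (14/16 = −12.5%, 16/18 = −11.1%, 18/20 = −10.0%). Two-year compliance reads 32/30 = 106.7%, 36/34 = 105.9%, 40/38 = 105.3%.
- Year 2 rule in both years: totals 28, 32, 36 (280/85 = 3.29, 320/95 = 3.37, 360/105 = 3.43 mg/kg). The Year 1 plan is 2 tablets high (16/14 = +14.3%, 18/16 = +12.5%, 20/18 = +11.1%). Two-year compliance reads 28/30 = 93.3%, 32/34 = 94.1%, 36/38 = 94.7%.

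**The case against.** The strongest reply is that whole tablets force some unevenness. Totals of 30, 34 and 38 over four treatment weeks are 7.5, 8.5 and 9.5 per week, so some weeks must be one tablet lower, and the SAP has merely put both low weeks in Year 2. Where they belong is a matter for the US label, which is not in the documents. Whole-tablet rounding makes unequal weeks necessary, but not unequal years: 8+7, 9+8 or 10+9 fits within each year and matches the protocol's equal courses. A formula giving one count for both weeks of a year cannot express that.

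A second reply is that the Year 2 counts are not uniformly low. The nearest whole number to 1.75 × weight / 10 equals the SAP's Year 2 count up to about 82.9 kg in the first band, 94.3 kg in the second and 105.7 kg in the third, which is 12.9 of the 30 kg (43%). At 105 kg, 18 tablets (1.71 mg/kg) are nearer 1.75 than 19 (190/105 = 1.81). The arithmetic is right, but where Year 2 is right on that measure, Year 1 is 2 tablets high, so the inconsistency remains.

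Three limits stand. The equal split is inferred from the yearly target, not read from a dosing table. The documents alone cannot fully exclude a wrong two-year total, and if the label itself had the SAP's split, the counts would be right and only the protocol's description loose. Finally, compliance is defined as total over total with no statement that it is computed by course or week, so the figures away from 100% on the equal split are conditional.

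**Conclusion.** The concern holds, as a minor point. That the planned years are unequal for 80 to <110 kg, against equal yearly courses in the protocol, follows from the documents alone. The two-year totals lie close to 3.5 mg/kg, which points to the split between years rather than the total. On the assumption of an equal split, each year's plan is off by 1 tablet (5.3% to 6.7%).

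The certain effect is on planned tablets and planned mg/kg for this band. Compliance is distorted only if it is computed by course, for the affected week, or with a Year 1 denominator for patients who stop early. Actual dose comes from the eCRF and is unaffected, as is the primary ARR calculation. Two-year compliance is unaffected provided the SAP's totals are right. The share of patients in this weight band is not given, so the effect on study-level summaries cannot be sized.

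**What to change.** Replace the two yearly formulae in SAP 13 with a table of planned tablets by weight band, year and treatment week, with weeks 1 and 2 listed separately, taken from the dosing table in the US prescribing information. Recompute planned mg, planned mg/kg and compliance from it. The table settles the counts whichever assumption above is true. State also whether compliance is reported by course or only over both years, and which denominator applies to patients who stop after Year 1.

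The cost is one SAP table, one sentence and a small programming change before database lock. No new data are needed.
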